***Exclusion Criteria***

1. Ongoing insulin therapy
2. Endoscopy within past 6 weeks
3. Use of anti-obesity drugs, or less than 3 months of discontinuation
4. Serum creatinine levels higher than 1.5 mg/dL
5. Hepatic enzyme elevation > 2x the upper limits of normal

6. Pregnant
7. Abnormal ECG
8. Prior bariatric surgery
9. Prior surgery on the alimentary tract
10. Gastroparesis
11. Inflammatory bowel disease
12. Currently using "blood thinners"
13. Pre-existing cardiovascular diseases
  - Heart attack in the past 3 months
  - Cardiac stenting
  - Heart valve disorders
14. Liver failure

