### 3.2 Previous Human Studies

Botox for injections has been approved for treatment of overactive bladder (idiopathic or neurogenic detrusor over activity), upper and lower limb focal spasticity, cerebral palsy, primary axillary hyperhidrosis, strabismus, blepharospasm, cervical dystonia, and chronic migraine ( $\geq 15$  days per month with headaches lasting 4 hours or more a day).

Adverse reactions experienced in each of these approved conditions have been listed as under. In general, adverse reactions occur within the first week of injection.

[figure not shown]

Fig 4. OGTT in DIO mice before and after Botox injection (3U/kg). (A) Blood glucose before (baseline,  $n=14$ ) and 28 days after saline ( $n=6$ ) or Botox injection ( $n=8$ ). (C) Glucose AUC before and after Botox injection. \*,  $p<0.05$ ; \*\*,  $p<0.01$ .

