**Strabismus:**

Strabismus patients receiving higher doses of BOTOX reported vertical deviation. About 17% of 2058 adults that received a total of 3650 injections for treatment of horizontal strabismus reported vertical deviation. Ptosis was reported in 1%, 16%, and 38% after injections in inferior rectus, horizontal rectus, and superior rectus, respectively. Retro bulbar hemorrhage was reported in 0.3% cases.

In general, local muscle weakness appears to be the most commonly reported and expected event following BOTOX injection in muscles. However, weakness of adjacent muscle tissues, and rarely remote tissues occurring as a result of “spread of toxin effect” have been reported in adult and pediatric patients as well. Events typically observed after any injection procedure including localized pain, inflammation, tenderness, bruising, erythema, and needle-related pain or anxiety have been reported in some clinical trials.

We will recruit obese subjects with pre-diabetes or T2D for the proposed clinical study for 5 visits. After informed written consent is obtained, subjects will be admitted to the Clinical Research Center (CRC), and will undergo upper endoscopic injection of Botox into the duodenal wall. We anticipate that injections of Botox into the duodenal wall will result in significant weight loss and improvements in glucose tolerance and duodenal nutrient sensitivity. Subjects will be studied over a period of 6 months. Subjects will be asked to complete 5 study visits: On the first visit, each subject will undergo an oral glucose tolerance test (OGTT). At visit 2, subjects will undergo an esophagogastroduodenoscopy (EGD) procedure for the delivery of BtX-A to the duodenal wall. Visits 3-5 will be made 1, 3, and 6 months after EGD (Figure 1). On every study visit, body weight and body composition will be recorded and oral glucose tolerance test (OGTT) be performed. Nutrient sensing test will be performed at visits 1 and 3.

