#### **4. Inclusion/Exclusion Criteria**

***Inclusion Criteria***

1. Age = 18-65
2. BMI  $\geq 30 \text{ kg/m}^2$
3. Having established diagnosis of Type 2 diabetes or pre-diabetes

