### 8.2. Protections against risk

(a) Minimizing physical, psychological, and social risks. Participation in this study is completely voluntary. Subjects will be free to drop out of the study due to any issues related, but not limited to physical discomfort, pain or other adverse events (AEs). Screening will be performed by a physician or nurse staff to ensure appropriate selection criteria are employed. Subjects will be free to refuse to respond to any question that may result in psychological disturbance. All patient care information utilized will be confidential and anonymous.

(b) Minimizing risks to confidentiality.

- All records and data will be de-identified and securely stored in Vanderbilt’s HIPAA-compliant, password protected data base, REDCap®; this is a secure web application for collection and management of clinical trial data developed by Vanderbilt University in collaboration with a vast consortium of thousands of active institutional partners.
- The subject’s identification is concealed, and a number is used as the identifier instead of the name. Only the PI, co-investigator, and research assistant will have access to identifiable private information. The PI will be responsible for maintaining the repository

and the identity of the samples. De-identified specimens will be released by the PI to projects after IRB approval only. Any paper documents will be stored in the PI's locked officer. All research samples (serum and plasma) obtained will be de-identified and stored in our locked freezers for an unlimited period of time. Only research personnel associated in our laboratory who are directly involved with the study will have access to research samples.

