### **(d) Data Safety Monitoring Plan (DSMP).**

- Our DSMP will focus on performance, safety, and care of participants. [name], Columbia University, and [name], Washington University St. Louis, will serve as the Data Safety Monitoring Board (DMSB) for this study.
- This is a pilot study. The DSMB will meet with the PIs at least 3 times. We are planning to initially enroll 3 patients and have the DSMB look at the efficacy and safety data. This will involve an initial meeting to ratify the DSMB, a meeting after the first patient undergoes EGD, and after 3 patients complete enrollment. The next meetings will be at the end of the first and second years, respectively. Progress reports will indicate patient recruitment status, adverse event occurrence, and summary of data collected. The DMSB will assess safety data including development of local or peripheral muscular weakness, bleeding, inflammation, hospitalizations, and other serious adverse events. Based on safety reports, the DMSB will advise and consent modification or termination of the study protocol or the study if it deems such actions to be warranted. Each meeting will be virtual, via zoom. We will send minutes to DSMB members for review and approval after each meeting.
- Participating subjects will be monitored by the physician and nursing staff of the VGIES PACU after recovering from anesthesia for EGD procedure and evaluated by physician prior to discharge.
- The research coordinator will be required to be present to record any AEs and report to the PI or co-investigators promptly of such events.

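### Eligibility does not address other botulinum toxin treatment, so weakness in a subject treated elsewhere, or with unrecorded existing weakness, could not be reliably attributed to the duodenal injection

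*Combined protocol and SAP*

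**What the plan says.** Section 4 has three inclusion criteria: age, BMI and "Having established diagnosis of Type 2 diabetes or pre-diabetes". Of its 14 exclusions, two set a time window on a recent exposure: "Endoscopy within past 6 weeks" and "Use of anti-obesity drugs, or less than 3 months of discontinuation". The nearest to muscle function is "Gastroparesis". Botulinum toxin is not mentioned, and neither is muscle weakness.

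Section 3.2 sets out other uses of the drug, beginning "Botox for injections has been approved for treatment of overactive bladder" and going on to limb spasticity, chronic migraine, cervical dystonia, axillary hyperhidrosis and eye conditions. On reactions away from the injected muscle it says "However, weakness of adjacent muscle tissues, and rarely remote tissues occurring as a result of" toxin spread have been reported. Section 7 repeats weakness as the drug-related risk of this study.

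Section 9(d) states: "The DMSB will assess safety data including development of local or peripheral muscular weakness", followed by bleeding, inflammation, hospitalizations and other serious events. It schedules a board meeting after the first patient's endoscopy and another after three patients.

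On screening outside Section 4, Section 8.2 says only: "Screening will be performed by a physician or nurse staff to ensure appropriate selection criteria are employed".

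**The concern.** The plan limits two kinds of recent exposure that could confuse its results, but not exposure to the study drug from another source. Its own list of indications makes such exposure foreseeable in adults aged 18-65, and recruitment is broad (employee lists, social media, a bariatric clinic census).

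Interpretation of safety is at stake. Section 11 compares each subject before and after a single intervention, and no section describes a control group. If weakness appears, there is no comparison rate, so attribution depends on what is known about that subject. If the subject also had Botox elsewhere, or was already weak, and nobody recorded it, the board cannot tell a study effect from an outside one. The problem is sharpest at the early looks, where each subject carries most weight.

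**Working it through.** The plan states no figure on this point, so there is nothing to reproduce. The check is a reading of every place where a safeguard could sit, followed by some simple arithmetic on size.

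**1. Is there a safeguard anywhere?**

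| Place | What it covers | Toxin exposure or existing weakness? |
|---|---|---|
| Section 4, inclusion (3) | Age, BMI, diabetes status | No |
| Section 4, exclusion (14) | Insulin, endoscopy, anti-obesity drugs, creatinine, liver enzymes, pregnancy, ECG, bariatric surgery, other alimentary surgery, gastroparesis, inflammatory bowel disease, blood thinners, cardiovascular disease, liver failure | No |
| Section 5 | Initial eligibility screen by study staff; stopping oral diabetes drugs before visits | No |
| Section 6, visit 1 | Standard physical examination, body measurements, blood tests, questionnaire | No toxin history; no neuromuscular assessment specified |
| Section 6, visits 3-5 | Weight, body composition, intake, glucose tolerance | No |
| Section 8.1 | Recruiter reviews the listed criteria | Adds none |
| Section 8.2 | Refers back to the selection criteria | Adds none |

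**2. Apply the list to a subject.** Take a 45-year-old with BMI 34 and pre-diabetes, otherwise healthy, who had Botox for chronic migraine last week. All three inclusions are met and none of the 14 exclusions applies. The same is true if the next migraine course is due two months after the study injection.

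**3. Can an outside course bring in the monitored event?** In Table 3 (chronic migraine), muscular weakness was reported in 24/687 = 3.5% on Botox and 2/692 = 0.3% on placebo. So a course given elsewhere can produce the event that the board watches. That is all these counts are used for here.

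**4. Weight of one such subject.** Planned enrolment is 20 (Sections 5 and 11).

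- Full sample: 1/20 = 5%.
- Look after three patients: 1/3 = 33%.
- Look after the first patient: 1/1 = 100%.

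**5. Chance that at least one is enrolled.** The share p of recruits with outside toxin exposure or existing weakness is not in the documents, so a range is assumed. With n independent recruits the chance is 1 − (1 − p)^n.

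| Assumed p | n = 20 | n = 3 |
|---|---|---|
| 1% | 1 − 0.99^20 = 18% | 1 − 0.99^3 = 3% |
| 2% | 1 − 0.98^20 = 33% | 1 − 0.98^3 = 6% |
| 5% | 1 − 0.95^20 = 64% | 1 − 0.95^3 = 14% |
| 10% | 1 − 0.90^20 = 88% | 1 − 0.90^3 = 27% |

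These are chances of enrolling such a subject, not of a weakness event.

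**6. Do the documents show more weakness with more toxin?** No. In Table 4 (upper limb spasticity), weakness was 0/115 = 0% at 251-360 units and 7/188 = 3.7% at 150-250 units. The accompanying text reports similar type and frequency of events at 400 units or more, or over four consecutive treatments in about a year. The under-150-unit column was left out because its printed N of 188 does not fit its percentages: 1/188 = 0.5% against a printed 2%, and 5/188 = 2.7% against a printed 9%.

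**The case against.** The strongest reply is that timing and site will usually settle the cause. Section 3.2 says that reactions generally occur within the first week, and Section 7 says that almost all of the weakness disappears in about 3-5 days. Calls are planned at days 1 and 7, with a telephone contact one week after the procedure. The visit 1 examination might also reveal overt weakness. This stands in part: attribution is impaired, not impossible. But timing helps only if the dates of the other course are known, and nothing requires anyone to ask. A course given close to the study injection overlaps with it in any case. An examination finding would trigger no criterion.

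A second reply is that such recruits may be rare. That stands as an unknown; the range in the working rests on assumed shares.

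A third concerns harm. A reader might infer that combined exposure makes toxin-spread weakness more likely, by adding the study's 100 units to doses given elsewhere or by reading the Table 3 rates as the effect of extra toxin. The documents do not support this. Table 3 compares Botox with placebo, not two courses with one. Summed units ignore site and elapsed time, while Section 1 describes limited diffusion from the injection site. Table 4 and its text show no rise with dose or repetition.

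A reader might also infer that neuromuscular disease raises the risk, or that an allergy criterion is missing. No section supplies evidence for either, so neither is part of this point. Existing weakness matters here only because it confounds a monitored safety item.

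**Conclusion.** The concern holds as a gap in eligibility and in recorded history. As written, Section 4 admits a subject with recent or planned botulinum toxin treatment, and no other section prevents or records it. In a one-group pilot of about 20, local or peripheral weakness in that subject, or in one with unrecorded existing weakness, could not be reliably attributed to the duodenal injection. One such subject is 5% of the full sample and one third of the data at the three-patient look.

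The conclusion rests on the text of the criteria and on the absence of a comparator; it needs no assumption about dose. How often the problem would arise is unknown. The documents do not quantify any added risk to the subject from combined exposure, and none is claimed. The change is worth making before enrolment because it affects who enters and costs very little.

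**What to change.** - Add to Section 4 an exclusion for botulinum toxin treatment, therapeutic or cosmetic, within a stated washout before the study injection, or planned during the 6-month follow-up. The sponsor and investigators should set the washout and give its basis. Section 12 does not supply one: it treats the duration of action in human gut muscle as open.
- At visit 1, record any previous toxin treatment (date, site, units) and any existing muscle weakness. The investigators should decide, and state in Section 4, whether existing weakness excludes.
- At visits 3-5, ask about toxin treatment received outside the study.
- Include these records in the safety reports to the board, so that any weakness event is read beside them.

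The cost is a short wording change, a few questions on the screening and visit forms, and possibly a few lost candidates.

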## 5. Screening and Enrollment

Obese subjects ( $\text{BMI} \geq 30 \text{ kg/m}^2$ ) with prediabetes or type 2 diabetes ( $n = 20$ ) will be recruited by solicitation flyers, recruitment emails using Research Match and LISTSERV that reaches all Vanderbilt employees, residents, and students, and Facebook advertisements. Subjects who do not qualify for bariatric surgery, or subjects who are awaiting insurance approval for a bariatric procedure at the Center of Surgical Weight Loss, One Hundred Oaks (OHO) at Vanderbilt University Medical Center will also be contacted via emails and telephone calls.

Subjects will undergo an initial screen by the study coordinator or research staff to assess eligibility and ability to comply with the study requirements. Prior to each study visit, subjects on oral anti-diabetic medications will be asked to discontinue these medications 4 days prior to their study visit. Diabetic subjects will be instructed to monitor their pre-prandial blood glucose during this time and to contact the study physician if their blood glucose levels are greater than 250 mg/dL for two consecutive readings. The study physician may instruct the subject to initiate short-term insulin therapy or resume their oral anti-diabetic medications; in either case the subject will be excluded from the study. Subjects will be instructed to maintain their usual diet and physical activity levels for 1 week prior to each study visit and to arrive fasted for every visit (only water after dinner).

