### Study visit 1:

#### Day 1:

- Subjects will arrive to the CRC after an overnight fast.

- They will undergo standard physical examination; anthropometric measurements (height, weight, waist and hip circumference) perform body composition assessment via DEXA imaging (dual-energy x-ray absorptiometry) will be recorded.
- *Baseline glucose tolerance* will be assessed by an oral glucose tolerance test (OGTT).
- Subjects will be handed a visual analog scale (VAS) questionnaire designed to capture their perceived hunger and satiety sensations, food preferences, cravings, and feeding behavior prior to intervention. The questions will be explained by the researcher and subjects will be instructed to bring in the completed questionnaire on their second visit.
- Subjects will be provided snacks and asked to return to CRC at 7 pm for the nutrient sensing test to be performed the following day. The subject will be fed a standardized meal and restricted to water after 8:00 pm.

## Day 2

- Blood will be drawn for determination of fasting plasma insulin, C-peptide, CBC, CMP, lipid profile, liver enzymes, PT, PTT, and gut hormones including ghrelin, GIP, GLP-1, pancreatic polypeptide (PP) and PYY.
- Subject will then consume a standardized 250 kcal liquid mixed meal containing 40 g carbohydrates, 6 g fat, and 9 g protein (8 oz. Ensure; Abbott Nutrition, Columbus, OH) within 10 minutes. Blood will be drawn at 15, 30, 60, and 120 minutes after consumption following which subject will be discharged.

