## Study visit 2 (within 2 weeks after the first visit):

- Subjects will undergo esophagogastroduodenoscopy (EGD) procedure for the delivery of BOTOX to the duodenal wall, to be performed by [name] at the Vanderbilt Gastrointestinal Endoscopy Suite (VGIES). We have been exempted from Investigational New Drug (IND) regulation for the proposed testing by the FDA (letter attached).
- Subjects will be monitored in the VGIES for 30 minutes and discharged with instructions for follow-up and contact information of the physicians' team (Drs. [name], [name]).

**Telemedicine visit** (1 week after SV2): Study team member will contact subject by telephone to assess if there have been any adverse events from the study procedures completed thus far.

**Study Visits 3-5** (1, 3, and 6 months after EGD): On every study visit, body weight, body composition via DEXA, food intake, and feeding behavior will be recorded and post-absorptive OGTT will be performed. Nutrient sensing test will be repeated at visit 3.

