## Oral Glucose Tolerance Test (Study visits 1 and 3-5):

- **Day 0:** Subjects will be fasting overnight (and restricted to water only after 8 pm).
- **Day 1:** Blood will be drawn for determining fasting blood glucose levels. At 8:00 am subjects will drink Trutol™ 75 (Thermo Scientific), a solution of 75g dextrose in 300 ml of water in 10 minutes. Blood will be drawn at 15, 30, 45, 60, and 120 min post ingestion.
- The subject will be fed a standardized snack and discharged around noon.

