## Endoscopic delivery of BOTOX via EGD (Study Visit 2):

- Subjects will arrive fasted at the GI Suite in the main hospital at Vanderbilt University for the EGD procedure.
- Under the supervision of an anesthesiologist, subjects will be given combination of intravenous medications, so they fall asleep. [name] will then pass the endoscope,

a long, flexible tube with light, video camera and channel for small instruments including syringes through the esophagus and stomach, pylorus into the junction of the 1st and 2nd parts of the duodenum. Botox (100 units dissolved in 200 µL of sterile, preservative-free 0.9% Sodium Chloride, USP) will be injected along the medial (mesenteric) border, into the duodenal muscle wall.

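### Read literally, the 4-day oral anti-diabetic drug stop also applies before the EGD visit (visit 2), where no glucose or hormone test is scheduled

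*Combined protocol and SAP*

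**What the plan says.** Section 5 (Screening and Enrollment) sets the rule: "Prior to each study visit, subjects on oral anti-diabetic medications will be asked to discontinue these medications 4 days prior to their study visit". While off drug, diabetic subjects check their glucose before meals and call the study physician after two readings in a row above 250 mg/dL. The physician may start short-term insulin or restart the oral drugs, and "in either case the subject will be excluded from the study". The same paragraph tells subjects "to arrive fasted for every visit (only water after dinner").

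Section 6 numbers the EGD as a study visit: "Study visit 2 (within 2 weeks after the first visit"). Its listed content is the endoscopy, the injection, monitoring and discharge. The subsection on endoscopic delivery adds: "Subjects will arrive fasted at the GI Suite in the main hospital". One data item falls due then, the appetite questionnaire handed out at visit 1: "subjects will be instructed to bring in the completed questionnaire on their second visit".

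The metabolic tests have their own subsections. One is headed "Oral Glucose Tolerance Test (Study visits 1 and 3-5"). The nutrient sensing subsection is headed for visits 1 and 3 only. For visits 3-5, Section 6 says: "On every study visit, body weight, body composition via DEXA, food intake, and feeding behavior will be recorded and post-absorptive OGTT will be performed". The study overview at the end of Section 3.2 has a similar sentence, which puts body weight, body composition and an OGTT at every visit.

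**The concern.** The evident purpose of a drug stop is to measure glucose and gut hormones without the influence of oral anti-diabetic treatment. At visits 1, 3, 4 and 5 it does that. At visit 2 there is nothing of the kind to measure, and the documents give no other reason for stopping treatment for 4 days before an endoscopy.

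Staff who follow Section 5 to the letter would interrupt diabetes treatment a second time soon after visit 1, just before anesthesia, with no gain in data. They would also apply the linked exclusion rule there. A subject could then be excluded for going back to usual oral drugs, after completing all baseline testing and before receiving the injection. The stake is an avoidable treatment interruption and added burden for subjects on oral drugs.

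**Working it through.** The plan states no figure on this point, so the check sets the rule beside the schedule and counts.

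**Inputs**
- Study visits: 5, with the EGD as visit 2 (Section 3.2 overview; Section 6).
- Length of each stop: 4 days, no visit exempted (Section 5).
- OGTT: visits 1, 3, 4, 5 (Section 6, OGTT subsection).
- Nutrient sensing test: visits 1 and 3 (Section 6, nutrient sensing subsection).
- Visit 2: within 2 weeks after visit 1. Visits 3-5: 1, 3 and 6 months after the EGD (Section 6).

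**Rule against schedule**

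| Visit | Drug stop as written | OGTT | Nutrient sensing test |
|---|---|---|---|
| 1 | yes | yes | yes |
| 2 (EGD) | yes | no | no |
| 3 | yes | yes | yes |
| 4 | yes | yes | no |
| 5 | yes | yes | no |

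**Count**
- Lead-in days as written: 5 × 4 = 20.
- Lead-in days before a visit with a metabolic test: 4 × 4 = 16.
- Excess: 20 − 16 = 4 days, or 1 stop of 5.

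These are lead-in days, not net days off drug. The documents do not say when subjects restart treatment after a visit, so the net figure cannot be derived.

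**Spacing**
- Visit 1 to 2: at most 2 weeks.
- Visit 2 to 3: 1 month.
- Visit 3 to 4: 3 − 1 = 2 months.
- Visit 4 to 5: 6 − 3 = 3 months.

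The stop that serves no test falls in the shortest gap in the schedule.

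**Does another sentence put a test at visit 2?** Only the Section 3.2 overview could be read that way. Its sentence comes directly after the one describing visits 3-5, and the dedicated OGTT subsection leaves visit 2 out. The more specific text governs. The questionnaire due at visit 2 is not a glucose or hormone measurement.

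**Effect on the analysis.** Section 11 compares pre-intervention values with those at 1, 3 and 6 months for body weight, gut-peptide AUC and glucose AUC. The visit 2 procedures supply none of these, so removing the stop there changes no endpoint analysis.

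**The case against.** **It may be loose wording.** The protocol refers to every study visit in places where it cannot mean all five; the Section 6 sentence quoted above stands under a heading for visits 3-5 only. The drug-stop sentence may follow the same habit. The fasting instruction in the same Section 5 paragraph does reach visit 2, but that is weak evidence of intent, because the endoscopy subsection sets fasting in its own right. This objection stands as to intent. It does not remove the need for a correction, because nothing in Section 5 tells staff to skip visit 2.

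**Some hold before the EGD may be wanted.** Subjects are fasted and given intravenous medication under an anesthesiologist. A hold of some length is plausible, so the 4-day excess is an upper bound. A hold for anesthesia would not, however, explain excluding a subject for resuming usual oral drugs.

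**The extra stop may do some good.** Anyone reaching visit 2 has already completed one stop without exclusion. Some who would fail a second stop might fail at visit 3, 4 or 5 anyway. For them, failing before the injection spares them an experimental procedure and avoids losing a dosed subject. This is a real, if small, cost of the change.

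**A reader might infer a loss of subjects or power.** Section 11 needs up to 16 subjects and plans 20, leaving 20 − 16 = 4 for attrition, so one unreplaced exclusion would use a quarter of that. The documents do not support taking this further. They give neither the share of subjects on oral drugs (prediabetic subjects are eligible) nor an exclusion rate per stop, and they do not say whether excluded subjects are replaced. Purely as an assumption, let all 20 take oral drugs, with a constant, independent exclusion risk p per stop and no other attrition. Expected completers are then 20(1 − p)^5 with five stops and 20(1 − p)^4 with four:
- p = 1%: 19.0 against 19.2.
- p = 5%: 15.5 against 16.3.
- p = 10%: 11.8 against 13.1.

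The difference runs from about 0.2 to 1.3 subjects and depends entirely on the assumed p. It also ignores that subjects at visit 2 have already tolerated one stop. It is not evidence of a retention problem.

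**Conclusion.** The point holds as a minor safety and burden issue. Taken literally, Section 5 applies the drug stop and its exclusion rule before visit 2, where Section 6 schedules no OGTT or nutrient sensing test. One of five stops is therefore an avoidable interruption of treatment, of up to 4 of 20 lead-in days, for subjects on oral anti-diabetic drugs.

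This rests on two readings: that the sentence in Section 5 means what it says, and that the specific test subsections in Section 6 override the general sentence in Section 3.2. If the sponsor never meant the stop to cover visit 2, what remains is a wording correction.

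The glucose monitoring and the physician's discretion over insulin or resumption limit the harm. No retention effect can be quantified, and no endpoint analysis is affected. Whether subjects already dosed should be excluded under the same rule at visits 3-5 is a separate question, and nothing here depends on it.

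**What to change.** 1. In Section 5, limit the 4-day stop, and the exclusion that follows insulin or resumption of oral drugs, to visits with an OGTT or nutrient sensing test: 1, 3, 4 and 5.
2. Let the study physician and anesthesia team set any shorter drug hold before the EGD. State that resuming usual oral drugs before visit 2 does not exclude a subject.
3. Keep home glucose monitoring before the EGD, with the call to the study physician for readings above 250 mg/dL. Section 5 ties that monitoring to the stop, so it would otherwise lapse when the stop is removed.
4. Do not waive the insulin consequence outright. Have the physician re-check eligibility before dosing anyone newly started on insulin, because ongoing insulin therapy is exclusion criterion 1 in Section 4.
5. In the Section 3.2 overview, align the sentence on body weight, body composition and OGTT with visits 1 and 3-5.

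The cost is a short wording amendment and a brief pre-EGD drug instruction. No scheduled glucose or hormone data are lost. The one downside is the loss of an off-drug check before dosing that might have identified subjects who would fail a later stop.
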